10.11 General Notes

- In case of death, a comprehensive narrative report of the case should be prepared by the Investigator and sent to the [REDACTED] Safety Contact by fax together with the Serious Adverse Event form, retaining a copy on site.
- If an autopsy is performed, copy of autopsy report should be actively sought by the Investigator and sent to the [REDACTED] Safety Contact as soon as available, retaining a copy on site.
- All source documents provided by the Investigator or site staff to the [REDACTED] Safety Contact must be carefully checked for respect of confidentiality. All personal patient's data must be redacted.

10.12 Independent Safety Monitoring Board

An Independent Safety Monitoring Board (ISMB) will be established to ensure the safety of study subjects on an on-going basis. The involvement of independent expert advisors will provide an unbiased evaluation

Clinical Study Code No.: CLI-06563AA1-02	Version No.: 6.0
IND No.: 131,339	Date: 18 March 2021

of the overall safety in the study, with particular regard to the incidence of major adverse outcomes (i.e. Serious Adverse Events) during and following study treatment administration.

Independent Clinicians (2 or 3) and one independent Biostatistician will compose the ISMB.

The Sponsor (and other study personnel) may be involved in some blinded parts of the ISMB meetings.

All ISMB members will keep as confidential all information and data deriving from the ISMB activity, without disclosing them to others.

The ISMB will have periodical face-to-face or telephone meetings, as appropriate, and meeting minutes will be issued after each meeting.

The complete ISMB guidelines including details regarding the members, duties and responsibilities, work and communication processes, frequency of meetings will be established by the ISMB members during the first meeting and reported in a separate charter.

11. DATA MANAGEMENT

An electronic CRF (eCRF) will be filled-in by the Investigator and/or his/her representative designee.

Front-end edit checks will run at the time of data collection and back-end edit checks will be used by the Data Manager to check for discrepancies and to ensure consistency and completeness of the data.

Subject questionnaires will be collected on paper and data will be entered at the site into the eCRF.

Medical history, adverse events and concomitant procedures will be coded using the MedDRA dictionary; medications will be coded using the WHO Drug dictionary and Anatomical Therapeutic Chemical classification (ATC). Access to electronic systems used for data collection will be granted to the study personnel only after appropriate training.

After the completion of data collection and cleaning, one or more data review meetings will be held to determine the occurrence of any protocol violation and to define the subject populations for the analysis. Although it will be possible to derive the treatment arm for patients who have reached or surpassed the end of the weaning phase, the explicit treatment codes will not be disclosed to the blinded team who are reviewing the data. All data review will occur without explicit access to treatment codes. Once the database has been declared to be complete and accurate, it will be locked, the randomization codes will be opened, and the planned statistical analysis will be performed. Of note, the randomization list will remain confidential from the blinded study team until after database lock, even for patients who are functionally unblinded.

If the database is unlocked after the initial lock, the process must be carefully controlled and documented; updates to the study data must be authorized by Chiesi.

At the study conclusion, a complete copy of the study data will be created for archival purposes at Chiesi. The investigators will receive copies of the patient data for retention at the investigational sites.

The 18-months (\pm 1 month) follow up data will be recorded in a separate database.

12. STATISTICAL METHODS

12.1 Sample Size

On the basis of the results of similar studies, it was determined that a sample size of 51 babies in (17 randomized to morphine and 34 randomized to CHF6563) will provide a power of 80% to detect a difference in duration of treatment of 13 days (312 hours), assuming a common standard deviation of 15 days and a two-sided significance level of 0.05. Assuming an early withdrawal rate of 10%, a total of 57 neonates will be randomized in order to reach a total of 51 evaluable babies completing the treatment period. Based on an assumed screening failure rate of 80%. It is anticipated that approximately 285 mothers should be pre-screened to achieve 57 randomized babies.

12.2 Populations for analysis

- **Enrolled Population:** all subjects for whom informed consent was signed.
- **Randomized Population:** all randomized subjects.
- **Intention-to-Treat population (ITT):** all randomized subjects who receive at least one dose of the study treatment and with at least one available evaluation of efficacy after the baseline.
- **Per-protocol population (PP):** all subjects from the ITT population without any major protocol deviations (i.e., wrong inclusions, non-permitted medications). Exact definition of major protocol deviations will be discussed by the study team during the review of the data and described in the Data Review Report.
- **Safety population:** all randomized subjects who receive at least one dose of study treatment.
 - The primary analysis population for efficacy will be the ITT. Analysis on the primary variable(s) will be repeated in the PP population
 - The Safety population will be used in the analysis of all safety variables.
 - In case of deviation between as-randomised treatment and treatment actually received, the treatment actually received will be used in the safety analyses (i.e. an as-treated analysis will be performed).

12.3 Statistical analysis

A detailed statistical analysis plan will be described in the Statistical Analysis Plan. The plan might be reviewed and updated as a result of the blind review of the data and will be finalized before breaking the blind.

12.3.1 **Descriptive Statistics**

General descriptive statistics for numeric variables will include the n (number of observed values), the mean, the standard deviation, the median, the minimum, and the maximum values. For categorical variables, the number and percent of subjects with a specific level of the variable will be presented.

12.3.2 **Missing data**

Babies for whom the parent/legal guardian wishes to discontinue treatment with study medication will be encouraged (via the parent/guardian) to remain in the study for collection of safety and efficacy data until the patient is discharged from the hospital or consent is otherwise withdrawn. These babies will receive standard of care according to clinical practice but will continue to contribute to study assessments. Handling of such cases will be described in the SAP.

Primary Efficacy Variable: Duration of treatment for babies who discontinue from the study prior to end of study treatment for any reason, including withdrawal due to treatment longer than 10 weeks, will be imputed using for the primary efficacy analysis. The imputed value will be the maximum of:

- the actual value for duration of treatment for the neonate (10 weeks for patients withdrawn due to treatment longer than 10 weeks) or
- the 90th percentile value for duration of treatment of all neonates, regardless of treatment group.

Further details on dealing with missing data, along with the handling of possible outliers, will be described in the Statistical Analysis Plan (SAP). Other critical missing data, if any, will be discussed during the review of the data. Decisions will be fully documented in the Data Review Report.

12.3.3 **Patient demographics and baseline characteristics**

Demographics and baseline variables will be summarized by treatment arm using descriptive statistics for the ITT population.

The following variables will be presented: gestational age, sex, race/ ethnicity, head circumference and percentile, weight and percentile, medical history, concomitant diseases, FNAST scores, primary feeding

CONFIDENTIAL

Clinical Study Code No.: CLI-06563AA1-02	Version No.: 6.0
IND No.: 131,339	Date: 18 March 2021

method, feeding type at randomization, duration of breastfeeding, maternal smoking, alcohol consumption, primary opioid and use of other licit and illicit drugs, prior medications (baby), and vital signs (neonate). Summary statistics of demographic and baseline characteristics will be presented for the Safety Population (if different from the ITT population) and the PP.

12.3.4 Primary efficacy variable

The primary efficacy variable is the duration of treatment defined as the number of hours from start of the treatment until the last dose of study drug.

An ANCOVA model based on log-transformed data will be performed to test the treatment effect as duration of treatment (hours).

The model will include treatment (CHF6563 and morphine) as a fixed effect and covariates for primary feeding method (formula/ any maternal breast- milk), Maternal primary opioid use (buprenorphine/ methadone / other), and maternal use of benzodiazepines, antidepressants or gabapentin (polypharmacy [yes/no]). In cases where observed primary feeding method during the treatment period (formula / any maternal breast milk) differs from the feeding method at time of randomization, the observed primary feeding method will be used for analysis. The adjusted geometric mean in each treatment group, the adjusted ratio of geometric means between treatments, together with its 95% CI and associated p-value will be estimated by the model.

Missing data handling for the primary efficacy analysis is described in [Section 12.3.2](#).

Sensitivity analyses will be performed as described in the SAP.

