Most relevant allowed concomitant treatments	Phenobarbital (only as adjunctive therapy). Acetaminophen administration for analgesia or treatment of pyrexia should not exceed 48 hours, with a maximum daily permitted dose of 60 mg/kg/day. During the weaning phase only: sedative and analgesia medications (including general and spinal anesthesia, skeletal muscle relaxants, benzodiazepines, and short acting opioids) required prior to or during

	
surgical, investigational and imaging procedures.
 
Any concomitant medication required for the standard care of babies will be permitted during the study.
 
Wherever possible post-operative analgesia should avoid systemic opioids; spinal / epidural analgesia, oral / parenteral acetaminophen and NSAIDS are permissible

Most relevant forbidden concomitant treatments	
Metabolic enzyme-inducing or inhibiting drugs, or drugs known to have a well-defined potential for hepatotoxicity should not be taken.
 
Other drugs which may give additive CNS/respiratory depression if used in combination with opioids (benzodiazepines, skeletal muscle relaxant, anticholinergics, etc.) unless required prior to or during surgical, investigational and imaging procedures undertaken.
 
Other drugs or biological substance to be administered under the provisions of a protocol on the same therapeutic target. Treatments for different conditions than NOWS and NAS may be permitted following an agreement with the Sponsor.

Breastfeeding	
Breastfeeding is allowed.
 
Current feeding status (formula or maternal breast milk [including combination of maternal breast milk and formula]) will be recorded just prior to randomization.
 
During the study, actual feeding will be collected in terms of breastfeeding, formula feeding, mixed feeding, and the proportion of feeding which is breast milk for subjects receiving both formula and breast milk.

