1. INTRODUCTION

1.1 Background information

Neonatal opioid withdrawal syndrome (NOWS) is a subset of Neonatal abstinence syndrome (NAS) and refers to neonatal withdrawal from opioid drugs and can occur in the presence of other drug withdrawal syndromes. In the United States, neonatal withdrawal following in-utero opioid exposure is typically the result of prolonged maternal use and/or abuse of illicit or prescribed opioids during pregnancy. Birth leads to the abrupt cessation of fetal substance exposure and can precipitate acute withdrawal symptoms that can result in severe health complications with prolonged recovery and longer hospitalization. Withdrawal can be both severe and intense, with an estimated 60% to 80% of exposed neonates requiring pharmacological intervention to control symptoms [1][2].

While the signs and symptoms of NOWS are similar to those experienced by adults undergoing acute opiate withdrawal, they present a higher risk to the neonate due to the babies' dependence on others for all aspects of well-being.

NOWS presenting signs include central nervous system hyperirritability (tremors, jitteriness, irritability, hyperactive muscle reflexes, and excessive high-pitched cry), autonomic nervous system deregulation and instability (tachypnea, nasal flaring, hyperphagia, temperature instability, insomnia, sweating, mottled skin, yawning, and sneezing), and gastrointestinal symptoms (diarrhea, vomiting, and poor feeding) [3][4][5]. Seizures are generally rare, although they have been reported occurring in 2% to 11% of neonate cases in the early stage of severe opioid withdrawal [6][7], especially if medical treatment has been delayed. A recent large observational cohort study of Medicaid babies in 46 US States reported an incidence of seizures was 2.7% among the 1705 observed cases of NAS [8]. Neonates with NOWS can also experience weight loss or failure to thrive, which often results from a combination of poor feeding, vomiting, nausea, and diarrhea [4][5]. If left untreated, some cases of NOWS may even lead to death [5]. Some of the less severe signs and symptoms of opiate withdrawal may persist for several months [3].

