3. STUDY DESIGN

This is a randomized, multicenter, double blind, double-dummy, parallel group, controlled study. Fifty-seven neonates with neonatal opioid-withdrawal syndrome (NOWS) with or without other concomitant drug withdrawal syndromes will be randomized to receive CHF6563 or morphine treatment. In order to maintain the blind, a double-dummy design will be used so that the subjects will receive either CHF6563 and morphine matched placebo, or morphine treatment and CHF6563 matched placebo.

The weaning period requires a lower number of weaning steps for CHF6563 compared to morphine. In order to avoid maintaining babies randomized to CHF6563 in the hospital following completion of study drug, only to receive placebo for several days (about 5, depending on the severity of the withdrawal), the unblinded pharmacist will advise the clinical staff that the baby has completed active study treatment following the last active dose of CHF6563 and babies will be eligible for discharge (at least insofar as the clinical trial is concerned) 48 hours after the last active dose. Since the cessation dose will not occur at the same weaning step for the 2 treatment arms, it will be possible to ascertain the treatment for each baby after the weaning step which corresponds to the cessation dose of CHF6563. This is considered a "functional unblinding" since, after this point, it will be possible for members of the blinded team to ascertain the treatment arm.

Prior to the last scheduled dose of CHF6563, all members of the blinded study team will remain completely blinded. Following the last scheduled dose of CHF6563/placebo, members of the blinded study team will not have access to the explicit treatment codes, but it will be possible to ascertain the treatment arm. Similarly, data review will occur without access to explicit treatment codes, since the explicit treatment codes will be maintained in a confidential manner. The randomization list and explicit treatment codes will be disclosed to blinded study team members only after the database is locked.

Clinical Study Code No.: CLI-06563AA1-02	Version No.: 6.0
IND No.: 131,339	Date: 18 March 2021

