6.5 Treatment allocation

Babies will be assigned in a 2:1 ratio to either CHF6563 or morphine. Randomization will be stratified according to the following variables, using a dynamic randomization algorithm (i.e. minimization) to balance treatment arms with respect to stratification factor levels, while maintaining an overall treatment balance:

- Neonate's feeding status at time of randomization (formula/ any maternal breast- milk [including combination of breast milk and formula])
- Maternal primary opioid use (buprenorphine/methadone/other)
- Maternal concurrent use of benzodiazepines, antidepressants or gabapentin (polypharmacy [yes/no]); please refer to [APPENDIX 3 – List of PSYCHOTROPIC DRUGS](#) for the list of drugs to be checked.

Clinical Study Code No.: CLI-06563AA1-02	Version No.: 6.0
IND No.: 131,339	Date: 18 March 2021

The minimization method is planned in order to maximize the balance of each stratification variable as well as the overall treatment balance across arms in a 2:1 ratio, considering the planned sample size [37]. This method achieves a greater level of balance across multiple stratification variables compared to a traditional stratified randomization

Babies will be centrally assigned to one of the two treatment arms on randomization through an IRT system (Interactive Response Technology, combination of voice and web response system and also referred as IVRS/IWRS).

Following 2 consecutive FNAST with a sum ≥ 12 , if all eligibility criteria except for Inclusion Criterion #5 are met, then babies will be pre-randomized in the IRT system to ensure treatment is available should Inclusion Criterion #5 be met (i.e. the sum of 3 consecutive FNAST scores ≥ 24 or a single score ≥ 12).

The IRT will allocate the patient to a certain treatment group using biased coin application of the Pocock and Simon minimization algorithm [37], and assign the study medication kit number corresponding to the babies' treatment group. IRT specifications will be fully described in a specific document. The IRT will also generate a confirmation after every IRT transaction is performed.

The patient will be identified by a unique number of six digits: the investigational site number will be the first three digits and the following three digits will be the progressive numbering of the patient within each site (e.g. 101001, 101002 etc.).

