7. STUDY PLAN

7.1 Study Schedule

The mothers of potential infants will be identified through the outpatient maternity, treatment clinics or upon admission to hospital. All babies for whom consent has been obtained will have NOWS graded according to FNAST. Pharmacological treatment will start up to 7 days after delivery in neonates who have persisting signs of NOWS despite the implementation of appropriate non-pharmacologic care. If all the inclusion/exclusion criteria are met the baby will be eligible for the randomization.

Following 2 consecutive FNAST with a sum ≥ 12 , if all eligibility criteria except for Inclusion Criterion #5 are met, then neonates will be pre-randomized in the IRT system to ensure treatment is available should Inclusion Criterion #5 be met (i.e. the sum of 3 consecutive FNAST scores ≥ 24 or a single score ≥ 12). If eligibility is confirmed, the randomization will be confirmed in the IRT system and the baby will be treated.

Clinical Study Code No.: CLI-06563AA1-02	Version No.: 6.0
IND No.: 131,339	Date: 18 March 2021

The study will be conducted as follows for each baby:

- A pre-screening visit with the mother to explain the study and obtain the informed consent to participate in the study, and to confirm the use of opioid in the last month of pregnancy. This visit will be carried out during the last month of pregnancy or after delivery. The maternal screening questionnaire will also be completed.
- A screening visit on the neonates who show sign of NOWS. The visit will be carried out up to 7 days after delivery.
- A randomization visit to verify the eligibility of the neonate for inclusion in the study and to assign the neonates to a treatment and provide the first treatment administration.
- Treatment period: from randomization, up to 48 hours after the last dose. The treatment period can last up to 10 weeks (70 days) from the first treatment dose.

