7.2.2 Feeding Status

Feeding status will be collected daily from the electronic patient record. (Formula /breast milk or a mixed feeding and proportion of maternal breast milk intake).

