8. EFFICACY ASSESSMENTS

8.1 Primary Efficacy endpoint

Duration of treatment defined as the number of hours from first dose of study drug administration until the last dose of study drug.

8.2 Secondary Efficacy endpoints:

- Time to first weaning, defined as the number of hours from first dose of study drug administration until the first dose reduction
- Requirement for adjunctive drug therapy (phenobarbital) for signs of NOWS
- Total hours of treatment with adjunctive therapy
- Requirement for rescue doses (CHF6563 or morphine)
- Number of rescue doses administered per neonate
- Percentage of total amount of active study drug which is from rescue doses
- Length of opioid related hospital stay, defined as number of days from day of birth until 48 hours after the final dose of drug treatment for Nows
- Relapse of Nows, defined as experiencing recurrence of significant signs of withdrawal
- Incidence of readmissions, defined as readmission to hospital for Nows relapse

Clinical Study Code No.: CLI-06563AA1-02	Version No.: 6.0
IND No.: 131,339	Date: 18 March 2021

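### Does adjusting for feeding observed during treatment, instead of feeding at randomization, call for a change to the plan?

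*Protocol*

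**What the plan says.** Protocol 6.5 names "feeding status at time of randomization" as one of three minimization factors, and the synopsis (Breastfeeding) says that it "will be recorded just prior to randomization". The primary model in Protocol 12.3.4 is an ANCOVA on log duration with treatment, primary feeding method, maternal primary opioid and polypharmacy. Where the method observed during the treatment period "differs from the feeding method at time of randomization, the observed primary feeding method will be used for analysis". Protocol 12.3.5 applies the same rule to every secondary efficacy variable, and the synopsis states it twice. Using the observed value whenever the two differ amounts to always using the observed value.

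The timing is set elsewhere:

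- Protocol 7.2.2: "Feeding status will be collected daily from the electronic patient record".
- Protocol 7.1: "Treatment period: from randomization, up to 48 hours after the last dose".
- Protocol 8.1: "Duration of treatment defined as the number of hours from first dose of study drug administration until the last dose of study drug".
- Protocol 3: "The weaning period requires a lower number of weaning steps for CHF6563 compared to morphine". The same section puts the gap at about 5 days, depending on severity.

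SAP v2.0 was written after early termination. Section 2.1.2 provides only a listing for the primary endpoint, and section 2.2.3 rules out inferential statistics. Section 6.1 states that 7 subjects were randomized against 57 planned, that the objectives cannot be evaluated, that the ITT and PP sets are not defined, and that the SAP supersedes the protocol's analysis.

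**The concern.** A covariate in a randomized comparison should be fixed before treatment starts. This one is not, and the period over which it is observed is close to the outcome itself: a baby treated longer has more days on which feeding can change. CHF6563 needs fewer weaning steps, so the design itself makes the window longer on morphine. Protocol 1.1 lists poor feeding among the signs of withdrawal, so a link through severity is conceivable, although no passage connects withdrawal with the choice between formula and maternal milk.

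If switching depends on arm, or on duration when durations differ by arm, the adjusted ratio is no longer the randomized effect and can err in either direction. The covariate also stops matching the factor used in the minimization. The term primary feeding method is not defined in the available documents, so it is unclear whether any maternal milk, the predominant method or the last method decides. A value recorded before randomization is already available.

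**Working it through.** **1. The plan's own figures.** A two-sample t-test with a 13-day difference, SD 15 days and two-sided 0.05 gives 79.1% power at 16+32 and 81.6% at 17+34. The planned 51 is therefore reproduced, and 51/0.9 = 56.7 gives 57.

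The weaning gap of about 5 days also follows from the dose tables. Reductions of 15% needed to reach the cessation dose:

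| Level | CHF6563 from (µg/kg) | Steps | Morphine from (mg/kg) | Steps | Difference |
|---|---|---|---|---|---|
| Initial | 10 | 0 | 0.07 | 7 | 7 |
| +1 | 15 | 2 | 0.09 | 8 | 6 |
| +2 | 20 | 4 | 0.12 | 10 | 6 |
| +3 | 25 | 6 | 0.16 | 12 | 6 |
| +4 | 30 | 7 | 0.21 | 14 | 7 |

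Taking off about two days for the CHF6563 interval extensions leaves 4 to 5 days. If feeding switches at 0.01, 0.02 or 0.04 per day (assumed), five extra days add a switching chance of 1 - exp(-5 × rate) = 4.9%, 9.5% or 18.1%.

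**2. Switching that depends only on time on treatment.** All inputs here are assumptions, because the documents give none: morphine median 25 days, log SD 0.6, half the babies on breast milk at randomization, feeding effect -0.2 on the log scale, 2:1 allocation. Ratio estimated with observed feeding at 0.01 / 0.02 / 0.04 per day:

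| Reading of observed feeding | True 0.60 | True 0.50 |
|---|---|---|
| Any maternal milk at all | 0.599 / 0.602 / 0.608 | 0.498 / 0.501 / 0.508 |
| Predominant, all switches out of breast milk | 0.603 / 0.606 / 0.612 | 0.503 / 0.506 / 0.512 |
| Last, all switches out of breast milk | 0.606 / 0.612 / 0.619 | 0.506 / 0.512 / 0.520 |

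The first row runs from 0.498/0.50 = -0.4% to 0.508/0.50 = +1.6%. The largest entry is 0.520/0.50 = +4.0%.

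The last two rows depend on the direction of switching. With equal switching both ways they return to 0.599-0.601 for a true 0.60. With a true ratio of 1.0 no reading shifts.

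For scale, the standard error of the log ratio is 0.6 × √(1/17 + 1/34) = 0.178. Then ln(0.508/0.50)/0.178 = 0.09 standard errors and ln(0.520/0.50)/0.178 = 0.22.

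**3. Switching that depends on arm.** Suppose feeding affects duration by -0.3 on the log scale and babies leave breast milk at 40% on morphine and 20% on CHF6563. Observed breast-milk shares are 0.5 × 0.6 = 0.30 and 0.5 × 0.8 = 0.40. The true ratio is 0.600 × exp(-0.3 × 0.10) = 0.582, while the model reports 0.600, which is 3% too high. Reversing the arms gives 0.618 against 0.600, about 3% too low.

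In a harsher case, arm moves the log-odds of breast milk by ±1.2 and severity also drives feeding. A true 0.60 is then reported as 0.643 or 0.557 (about ±7%). With no true effect, rejection at 51 babies is 6.4% or 6.6%; with feeding at randomization it is 5.0% or 4.5% in the same runs.

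**4. Where the rule would act.** It would act only in the models of Protocol 12.3.4 and 12.3.5, and SAP v2.0 fits none of them. What remains is a label: SAP 4.3.1 and 4.3.3 tabulate primary feeding method with baseline characteristics. Feeding type at randomization stands beside it, so the pre-randomization value is still reported.

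**The case for a change.** The strongest case for acting is that the rule is explicit, appears four times and breaks a basic principle, while the repair would be wording only because the value at randomization is already collected. For time to first weaning it is plainer still: the feeding window continues after that endpoint has occurred, so the covariate may be measured after the outcome it adjusts. Blinding up to the last active CHF6563 dose limits a direct effect of arm on feeding, but not the duration and severity routes. SAP v1.0, which is not available, may have added an analysis with feeding at randomization, but that would not alter the primary model in the protocol.

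All of this stands as criticism of the model in protocol v6.0. It does not show that a change would alter anything in this trial, because the model is not run. Nor is the size established: the documents give neither a rate nor a direction of switching, and the arm-dependent rates are invented for illustration. There is also a small trade-off. Feeding status in the first week may predict later feeding poorly, so the value at randomization might explain less variance.

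**Conclusion.** No change is called for, because there is nothing to gain. The substitution is a genuine weakness of the protocol v6.0 models, and anyone reusing that text should adjust for feeding at randomization and keep observed feeding for description or a labelled supplementary model. In this trial, SAP v2.0 has replaced those models with listings after 7 of 57 babies, so no estimate, interval or p-value uses the covariate. The baseline label in the SAP matters only if primary feeding method means the observed value, and the value at randomization is tabulated with it.

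Had the models been run, a shift driven by time on treatment alone would have been about -0.4% to +1.6% on the literal reading and up to about +4% if all switching ran out of breast milk. It would have been about nil on the predominant and last readings with equal two-way switching, and nil on every reading with equal durations by arm. Against a standard error of 0.178 on the log scale, that is at most about 0.22 standard errors. Larger shifts, about 3% to 7% either way, need switching that differs by arm. The documents neither show nor exclude that.
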